## 9.2. Efficacy Variables

### Primary Efficacy Parameter:

Time from first dose to Sustained Response based on the FLU-PRO Patient Reported Outcomes Instrument.

### Secondary Efficacy Parameter:

### Proportion of subjects progressing to severe COVID-19 illness.

### Exploratory Efficacy Parameters:

- i. Proportion of subjects positive for SARS-CoV-2 by Aptima® SARS-CoV-2 Assay at Days 4 and 10.
- ii. Mean changes from baseline in quantitative SARS-CoV-2 RNA measured by RT-PCR .
- iii. Proportion of subjects hospitalized due to COVID-19 or complications thereof.
- iv. Proportion of subjects with mortality due to COVID-19 or complications thereof.

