## 3. STUDY OBJECTIVES

**Primary Objective:** To evaluate the effect of NTZ in reducing the time to Sustained Response compared to placebo in subjects with mild or moderate COVID-19

**Secondary Objective:** To evaluate the effect of NTZ in reducing the rate of progression to Severe COVID-19 Illness compared to placebo

**Exploratory Objectives:** To evaluate:

- The proportion of subjects positive for SARS-CoV-2 by Aptima® SARS-CoV-2 Assay at each of Days 4 and 10
- The change from baseline in quantitative SARS-CoV-2 RNA measured by RT-PCR at each of Days 4 and 10
- The effect of NTZ in reducing the rate of hospitalization compared to placebo
- The effect of NTZ in reducing the rate of mortality compared to placebo

Safety Objectives: Safety will be assessed by analysis of adverse events.

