### **8.1.9. Day 28 Subject Contact**

Site staff will contact each subject by telephone on study Day 28 to determine if the subject has experienced any new adverse events, developed severe COVID-19 illness, or required hospitalization for any reason.

If warranted, the Day 28 subject contact may also occur in-person at the clinic or another location as agreed upon by the site and subject.

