#### 9.4.1. Efficacy Analyses

Efficacy analyses will be based on a population consisting of all subjects randomized who receive at least one dose of study medication and are positive for SARS-CoV-2 by Aptima® SARS-CoV-2 Assay at Baseline. For time-to-event analyses, a test of significance (as described in the following) will be performed with descriptive statistics provided, including the use of Kaplan-Meier figures.

There will be one primary efficacy analysis:

- Time to Sustained Response for the NTZ treatment group will be compared to that of the placebo treatment group using a stratified Gehan-Wilcoxon test ( $\alpha=0.05$ ) where stratification will follow that used for randomization. Subjects without a Sustained Response recorded will be treated as censored as of the last diary without a documented Sustained Response, except for subjects who are hospitalized or die during the study, who will be censored at Day 21 (hour 504).

Sensitivity analyses for the primary efficacy analysis will be described in the Statistical Analysis Plan.

If the primary analysis is significant at the 0.05 level, the key secondary efficacy analysis will be formally evaluated at the 0.05 level as follows:

- Proportions of subjects progressing to Severe COVID-19 Illness will be compared between the treatment groups using a Cochran-Mantel-Haenszel (CMH) test stratified by the randomization strata.

Exploratory analyses will be performed as follows:

- Proportions of subjects positive for SARS-CoV-2 by Aptima® SARS-CoV-2 Assay at study Day 4 and Day 10 will be compared between the treatment groups using a Cochran-Mantel-Haenszel (CMH) test stratified by the randomization strata.
- Mean changes from baseline in quantitative SARS-CoV-2 RNA measured by RT-PCR at Day 4 and Day 10 will be compared using a t-test.
- Proportions of subjects hospitalized due to COVID-19 or complications thereof will be compared across the treatment groups using a CMH test stratified by the randomization strata.
- Proportions of subjects with mortality related to COVID-19 or complications thereof will be compared across the treatment groups using a CMH test stratified by the randomization strata.

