4.0 Analysis of Efficacy

4.1 Efficacy Variables

4.1.1 Primary Efficacy Variable

The primary efficacy variable is the Time to Sustained Response. This is defined as the time in days from the first dose of study medication to the time of the first diary entry meeting all the criteria for a sustained response (i.e., Time of Sustained Response).

Sustained response to treatment is defined as a decrease in the total FLU-PRO score from the previous, subject assessment that symptoms are at least “somewhat better than yesterday”, no oral temperature ≥ 100.4 F in the preceding 24 hours, and no future increase in any of the FLU-PRO domains except within the following levels:

FLU-PRO Domain	Background Level
Body/Systemic	0.56
Throat	0.67
Eyes	0.67
Gastrointestinal	2.00
Head	2.00
Nose	Larger of score at time of response or 0.75
Chest	Score at time of response
Cough	Larger of score at time of response or 1.75

Subjects must have at least one diary following the time of sustained response in which there is no relapse, meaning that a subject cannot achieve sustained response at the last diary entry.

Situation	Censoring rule
Has Time of Sustained Response	Not censored.
Hospitalized due to COVID-19	Censored at Day 21 (i.e., hour 504).
Died (any cause)	Censored at Day 21 (i.e., hour 504).
No Time of Sustained Response	Censored at time of last diary entry without sustained response.

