Viral RNA levels will be determined for the Day 4 and Day 10 nasopharyngeal swabs by quantitative RT-PCR. The reported value will be transformed by $\log_{10}(X+1)$, where X is the reported number of RNA copies/ μ L. The transformed values will be summarized with descriptive statistics (number of observations, mean, standard deviation, minimum, maximum, median) by treatment group. A Satterthwaite T-test will be used to test the hypotheses

$$H_0: \mu_{NTZ} = \mu_{Ctl}$$
$$H_1: \mu_{NTZ} \neq \mu_{Ctl},$$

where μ_{NTZ} and μ_{Ctl} respectively represent the mean $\log_{10}(\text{RNA copies}/\mu\text{L})$ concentrations for the NTZ and placebo groups. A 95% confidence interval for the difference in means will be provided.

4.2.2.4 Exploratory Analysis: Proportion of Subjects Hospitalized Due to COVID-19 or Complications Thereof

The cross-tabulation of Hospitalization due to COVID-19 illness or complications thereof versus treatment group will be provided, with conditional rates for each treatment group.

Hospitalization due to COVID-19 or complications thereof will be analyzed using a CMH test stratified by the randomization stratum with the appropriate continuity correction at an unadjusted α of 0.05. The hypotheses tested are

$$\begin{aligned} H_0: p_{NTZ} &= p_{Ctl} \\ H_1: p_{NTZ} &\neq p_{Ctl} \end{aligned}$$

where p_{NTZ} and p_{Ctl} respectively represent the rate at which NTZ subjects and placebo subjects are hospitalized due to COVID-19 illness or its consequences. The overall odds ratio and a 95% confidence interval for the odds ratio will be provided.

4.2.2.5 Exploratory Analysis: Proportion of Subjects with Mortality Due to COVID-19 or Complications Thereof

The cross-tabulation of Mortality due to COVID-19 illness or complications thereof versus treatment group will be provided, with conditional rates for each treatment group.

Mortality due to COVID-19 or complications thereof will be analyzed using a CMH test stratified by the randomization stratum with the appropriate continuity correction at an unadjusted α of 0.05. The hypotheses tested are

$$\begin{aligned} H_0: p_{NTZ} &= p_{Ctl} \\ H_1: p_{NTZ} &\neq p_{Ctl} \end{aligned}$$

where p_{NTZ} and p_{Ctl} respectively represent the rate at which NTZ subjects and placebo subjects die due to COVID-19 illness or its consequences. The overall odds ratio and a 95% confidence interval for the odds ratio will be provided.

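### The exploratory objectives on hospitalisation and mortality carry no cause restriction, but the only planned between-arm tests count events attributed to COVID-19, so the objectives are not answered as worded

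*Protocol*

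**What the plan says.** The exploratory objectives in Protocol section 3 include "The effect of NTZ in reducing the rate of hospitalization compared to placebo" and "The effect of NTZ in reducing the rate of mortality compared to placebo". The Protocol synopsis and SAP 1.0 repeat them, also without a cause.

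The variables in Protocol 9.2 add one: "Proportion of subjects hospitalized due to COVID-19 or complications thereof" and "Proportion of subjects with mortality due to COVID-19 or complications thereof". SAP 4.1.2 follows. The tests are restricted in the same way, with slightly different wording. Protocol 9.4.1 has "Proportions of subjects with mortality related to COVID-19 or complications thereof will be compared across the treatment groups", while SAP 4.2.2.5 defines its parameter as "the rate at which NTZ subjects and placebo subjects die due to COVID-19 illness or its consequences". Tables 14.2.6 and 14.2.7 carry the restriction in their titles. None of these sections gives a time window.

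Collection is broader. The Day 28 contact (Protocol 8.1.9) asks whether the subject "required hospitalization for any reason". Protocol 8.4.1 makes fatal events and in-patient admissions serious adverse events, and 8.4.4 calls for a narrative on any hospitalisation.

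**The concern.** Whether an admission or death in the weeks after infection was caused by COVID-19 is a judgement. An event judged unrelated, or judged to be caused by the drug, leaves the efficacy count. The attributed comparison therefore cannot by itself show the net effect on admissions or deaths that the objectives name. An all-cause count needs no such judgement and matches the objective as written.

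Neither document states an attribution rule. The investigator causality scale in Protocol 8.4.1 concerns relation to study drug, not to COVID-19. The data monitoring committee's stated role in Protocol 10.1.4 is safety and futility. At stake is how two exploratory results can be read, and whether a report can say that the stated objectives were addressed.

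**Working it through.** The plan gives no event count, power or sample size for either endpoint, so there is no figure of its own to reproduce. The check is a comparison of text, then of scale.

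**Text**

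| Step | Location | Scope |
|---|---|---|
| Objective | Protocol 1.1 and 3; SAP 1.0 | No cause stated |
| Variable | Protocol 9.2; SAP 4.1.2 | Attributed to COVID-19 |
| Between-arm test | Protocol 9.4.1; SAP 4.2.2.4 and 4.2.2.5; Tables 14.2.6 and 14.2.7 | Attributed to COVID-19 |
| Collection | Protocol 8.1.9, 8.4.1, 8.4.4 | Any cause |
| Other outputs | Table 14.3.1.5 (serious events by organ class and preferred term); Listings 16.2.6.3 and 16.2.7.3 | No all-cause comparison of either rate |

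**Expected hospitalisations, N × rate**

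N is 350 to 400 infected subjects (Protocol 9.1). Protocol 2.1 cites a background rate of 82 per 100,000 cases, and 255 per 100,000 over age 65.

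- 350 × 0.00082 = 0.29; 400 × 0.00082 = 0.33
- 350 × 0.00255 = 0.89; 400 × 0.00255 = 1.02
- Assumed 1% to 5%: 350 × 0.01 = 3.5; 400 × 0.05 = 20

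The documents give no corresponding death rate for subjects like these.

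**Weight of one attribution**

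Take hypothetical counts, 175 per arm and an unstratified Fisher exact test. For 0 versus k events, two-sided p = 2 × C(175,k) / C(350,k).

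- k = 1: p = 1.0
- k = 2: 2 × (175 × 174) / (350 × 349) = 0.50
- k = 5: p = 0.061
- k = 6: p = 0.030

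Moving one event crosses 0.05 only between 5 and 6, with every event in one arm. Among one or two deaths it changes nothing inferentially.

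**Population**

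SAP 2.2.1 makes ITI primary for all efficacy analyses, and Protocol 9.4.1 bases efficacy on infected subjects. SAP 4.2.2 assigns all key secondary and exploratory analyses to ITT, and Tables 14.2.6 and 14.2.7 agree with that. At the anticipated 50% to 75% positivity, 1 − 0.75 = 25% to 1 − 0.50 = 50% of enrolled subjects would be negative at baseline. At the upper end that is 800 − 400 = 400 people. An all-cause count in ITT would include their admissions.

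**The case against.** The strongest reply is that an objective is shorthand and the variable defines it. Protocol 9.2 does so explicitly, and later sections follow it consistently in substance. That stands in part: the attributed rate is a narrower answer, not a missing one. A reader might infer that the questions go unanswered altogether, and the documents do not support that.

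A reader might also infer that drug-caused or unrelated events disappear. They do not. Serious events are summarised by arm in Table 14.3.1.5, deaths are listed in 16.2.7.3, and hospitalisation status and mortality are listed in 16.2.6.3. What is missing is an all-cause rate by arm.

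A third inference is that attribution favours one arm. The sponsor, investigators, monitors and statisticians are masked (Protocol 6.3). The documents report chromaturia in 10.8% on drug against 0.8% on placebo, but they also provide a vitamin supplement to mask it. Nothing in them shows differential attribution. A rule may sit in the Medical Monitoring Plan or the committee charter, which are not among the documents reviewed.

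Finally, exclusion criterion 13 bars subjects expected to need hospitalisation unrelated to COVID-19. All-cause and attributed counts may therefore be close. That lessens the consequence, and it also lessens the dilution from adding the all-cause count.

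**Conclusion.** The mismatch is real and minor. The two objectives are not answered as worded, because every planned between-arm test depends on an attribution for which neither document states a rule, although the all-cause data will be in hand. Both endpoints lie outside the primary and key secondary sequence, so no error rate, sample size or primary conclusion changes.

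The size in events is uncertain. The low estimate rests on a cited background rate that was not offered as an assumption for this trial. The high estimate rests on an assumed 1% to 5%. How many admissions would be judged unrelated cannot be derived from the documents. A reader might infer that a single reattributed death would change the result; the Fisher values for 0 versus 1 and 0 versus 2 deaths show that it would not change a test at 0.05. The case for the change is that the analysis should match the objective and avoid a cause judgement, not that a conclusion is at risk.

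**What to change.** In SAP 4.2.2.4 and 4.2.2.5 and Tables 14.2.6 and 14.2.7:

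- Add all-cause hospitalisation and all-cause mortality through Day 28 by arm in the ITI population, with counts, rates and the same stratified CMH test and odds ratio. ITI is defined by a baseline swab, so restricting to it does not depend on treatment. With few events over eight strata, the counts and rates will carry most of the information.
- Keep the COVID-19-attributed versions alongside, and state or cross-reference who attributes events, by what criteria, and that this is done blind.
- Reconcile the ITI statement in SAP 2.2.1 with the ITT statement in SAP 4.2.2 and the table titles.

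Rewording the objectives to attributed rates would also remove the mismatch, but would leave the results resting on attribution alone.

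The cost is two extra tables from data already collected, a sentence on attribution, and some dilution by unrelated admissions, which exclusion criterion 13 should limit.

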### 9.3. Response Definitions

Sustained Response:

A decrease in total FLU-PRO score from the previous diary with patient assessment that symptoms are at least “somewhat better than yesterday”, no oral temperature  $\geq 100.4^{\circ}\text{F}$  in the prior 24 hours, and no future increase in any of the FLU-PRO domains except within the following levels:

FLU-PRO Domain*	Background Level
Body/Systemic	0.56
Throat	0.67
Eyes	0.67
Gastrointestinal	2.00
Head	2.00
Nose	Score at time of response or 0.75, whichever is greater
Chest	Score at time of response or 0.00, whichever is greater
Cough	Score at time of response or 1.75, whichever is greater

\* A diagram of the FLU-PRO domain/subdomain structure is attached as [Appendix 5](#).

Time of Sustained Response:

The time of the first diary at which all Sustained Response criteria are met.

Time to Sustained Response:

The time (hours) from the first dose of study medication and the Time of Sustained Response.

Severe COVID-19 Illness:

Subject must have (1) shortness of breath at rest and (2)  $\text{SpO}_2 \leq 93\%$  on room air or  $\text{PaO}_2/\text{FiO}_2 < 300$ .

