## 5.2. Exclusion Criteria

1. Persons with any clinical sign or symptoms suggestive of severe systemic illness with COVID-19, including the following:
  - a. shortness of breath at rest,
  - b. resting pulse  $\geq 125$  beats per minute,
  - c. resting respiratory rate  $\geq 30$  breaths per minute, or
  - d.  $\text{SpO}_2 \leq 93\%$  on room air at sea level.
2. Subjects who experienced a previous episode of acute upper respiratory tract infection, otitis, bronchitis or sinusitis or received antibiotics for these conditions within two weeks prior to and including study day 1.
3. Severely immunodeficient persons including:
  - a. Subjects with immunologic disorders or receiving immunosuppressive therapy (e.g., for organ or bone marrow transplants, immunomodulatory therapies for certain autoimmune diseases)
  - b. Subjects with untreated HIV infection or treated HIV infection with a CD4 count below 350 cells/mm^3 in the last six months
  - c. Subjects actively undergoing systemic chemotherapy or radiotherapy treatment for malignancy
  - d. Subjects using steroids as maintenance therapy for chronic conditions
4. Subjects with active respiratory allergies or subjects expected to require anti-allergy medications during the study period for respiratory allergies.
5. Females of childbearing potential who are either pregnant or sexually active without the use of birth control. Female subjects of child-bearing potential that are sexually active must have a negative baseline pregnancy test and must agree to continue an acceptable method of birth control for the duration of the study and for 1 month post-treatment. A double barrier method, oral birth control pills administered for at least 2 monthly cycles prior to study drug administration, an IUD, or medroxyprogesterone acetate administered intramuscularly for a minimum of one month prior to study drug administration are acceptable methods of birth control for inclusion into the study. Female subjects are considered of childbearing potential unless they are postmenopausal (absence of menstrual bleeding for 1 year - or 6 months if laboratory confirmation of hormonal status), or have had a hysterectomy, bilateral tubal ligation or bilateral oophorectomy.
6. Subjects with a history of COVID-19 or known to have developed anti-SARS-CoV-2 antibodies.
7. Subjects residing in the same household with another subject participating in the study.

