### **8.1.8. Day 2-7 Subject Contact**

Site staff will contact each subject by telephone on study Days 2-7 to verify:

1. Did the subject take all expected doses of study medication?
2. Did the subject complete all expected electronic diaries?
3. Does the subject have worsening symptoms or adverse events that warrant an unscheduled visit?
4. Does the subject have shortness of breath at rest? *If yes, instruct the subject to come to the clinic for an unscheduled visit to screen for progression of illness or refer to hospital as warranted. If the subject is referred to the hospital or emergency department, the Investigator will attempt to obtain hospital records indicating SpO2 or PaO2/FiO2 from the subject for the purposes of defining progression to severe COVID-19 illness. The SpO2 or PaO2/FiO2 obtained from hospital records will be entered on an Unscheduled Visit eCRF.*

If the subject has missed medication or electronic diaries, the site staff will re-train the subject on the importance of medication and diary compliance.

This contact may occur at the Day 4 or unscheduled visit in lieu of telephone contact.

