4.1.2 Key Secondary and Exploratory Efficacy Variables

The key secondary efficacy variable is Progression to Severe COVID-19 Illness. Any subject meeting both of the following criteria has advanced to Severe COVID-19 Illness:

1. Shortness of breath at rest.
2. $\text{SpO}_2 \leq 93\%$ on room air, or $\text{PaO}_2/\text{FiO}_2 < 300$.

The exploratory efficacy variables are:

1. Proportion of subjects positive for SARS-CoV-2 by Aptima® SARS-CoV-2 assay at Days 4 and 10.
2. Change from baseline of quantitative SARS-CoV-2 RNA measured by RT-PCR at Days 4 and 10.
3. Hospitalization due to COVID-19 or complications thereof.
4. Mortality due to COVID-19 or complications thereof.

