4.2.2 Key Secondary and Exploratory Efficacy Analysis

All key secondary and exploratory efficacy analyses will be performed for the ITT population.

4.2.2.1 Key Secondary Efficacy Analysis: Proportion of Subjects Progressing to Severe COVID-19 Illness

The cross-tabulation (i.e., two-way table) of Progression to Severe COVID-19 illness versus treatment group will be provided, with conditional rates of progression for each treatment group.

If the primary efficacy analysis is statistically significant at $\alpha=0.05$, the key secondary efficacy variable (Progression to Severe COVID-19 Illness) will be analyzed. The proportion of subjects in the NTZ and placebo groups experiencing progression to severe

COVID-19 illness will be analyzed using a CMH test stratified by randomization stratum with appropriate continuity correction at an unadjusted $\alpha=0.05$. The hypotheses tested are

$$H_0: p_{NTZ} = p_{Ctl}$$
$$H_1: p_{NTZ} \neq p_{Ctl},$$

where p_{NTZ} and p_{Ctl} respectively represent the rate at which NTZ subjects and placebo subjects progress to severe COVID-19 illness. The overall odds ratio and a 95% confidence interval for the odds ratio will be provided.

4.2.2.2 Exploratory Analysis: Proportion of subjects Positive for SARS-CoV-2 by Aptima® SARS-CoV-2 Assay at Days 4 and 10

Nasopharyngeal swabs for virology testing are scheduled to be taken on the Day 4 and Day 10 visits. The rates at which subject nasopharyngeal swabs test positive for SARS-CoV-2 in the NTZ and placebo groups will be analyzed using a CMH test stratified by the randomization stratum with the appropriate continuity correction at an unadjusted α of 0.05. The hypotheses tested are

$$H_0: p_{NTZ} = p_{Ctl}$$
$$H_1: p_{NTZ} \neq p_{Ctl},$$

where p_{NTZ} and p_{Ctl} respectively represent the rate at which NTZ subjects and placebo subjects test positive by the Aptima® SARS-CoV-2 assay. The overall odds ratio and a 95% confidence interval for the odds ratio will be provided. The cross-tabulation of SARS-CoV-2 status versus treatment group will be provided, with conditional rates for each treatment group. Day 4 and Day 10 data will be analyzed separately.

4.2.2.3 Exploratory Analysis: Changes from Baseline in Quantitative SARS-CoV-2 RNA Measured by RT-PCR

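### The key secondary endpoint has no death component and no rule for absent oxygenation records, so a COVID-19 death or admission can fall outside its definition of progression

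*Protocol*

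**What the plan says.** The key secondary parameter in Protocol 9.2 is "Proportion of subjects progressing to severe COVID-19 illness". If the primary analysis succeeds, Protocol 9.4.1 says that "the key secondary efficacy analysis will be formally evaluated at the 0.05 level". It is the only secondary endpoint with a formal test. SAP 4.2.2.1 specifies a CMH test stratified by randomization stratum, "with appropriate continuity correction at an unadjusted" alpha of 0.05.

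Protocol 9.3 defines the event: "Subject must have (1) shortness of breath at rest and (2", where item 2 is a room-air SpO2 of 93% or less, or a PaO2/FiO2 below 300. SAP 4.1.2 agrees: "Any subject meeting both of the following criteria has advanced to Severe COVID-19 Illness". Hospitalisation and mortality due to COVID-19 are separate exploratory endpoints, not components of this one.

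On ascertainment, Protocol 8.1.8 covers subjects referred to a hospital or emergency department: "the Investigator will attempt to obtain hospital records indicating" SpO2 or PaO2/FiO2. Under Protocol 8.4.4, care in hospital follows local standard of care. The Day 28 contact (Protocol 8.1.9) is by telephone unless an in-person contact is warranted.

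On missing data, SAP 2.3 deals with dates and SAP 4.2.1.3 with the primary diary endpoint. Neither addresses the key secondary.

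**The concern.** An endpoint meant to capture progression to severe disease should classify the most severe outcomes without ambiguity. Here classification depends on two recorded findings. One of them may be absent for the sickest subjects: a subject may die outside hospital, may be given oxygen before any room-air reading is recorded, or may be admitted to a hospital whose records the site cannot obtain.

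The sponsor did consider such subjects for the primary endpoint. The SAP 4.1.1 censoring table has a row for COVID-19 hospitalisation and a row "Died (any cause"), both placed at hour 504. The key secondary has no corresponding rule. At stake are the meaning of the one formally tested secondary result and, if events are few, which side of 0.05 it falls on.

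**Working it through.** **1. Applying the definition as written**

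| Subject | Meets both items? | Stated classification |
|---|---|---|
| Resting breathlessness, and qualifying room-air SpO2 recorded before oxygen was started | Yes | Progressed |
| Resting breathlessness, and qualifying PaO2/FiO2 recorded later | Yes | Progressed |
| COVID-19 death without both items on record | No | None beyond not meeting the definition |
| COVID-19 admission with no qualifying oxygenation value on record | No | None beyond not meeting the definition |

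In the last two rows the variable is yes/no, both criteria are required, and no imputation or exclusion rule exists. The direct result is a non-event. The only alternative is to treat the subject as missing, which the plan does not state either.

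**2. The denominator**

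Protocol 9.1 derives 312 subjects from the EV/RV curves and allows about 10% for dropout: 312/0.90 = 346.7, or 347, against the stated minimum of 350. SAP 1.3 gives 175 per arm. The 312 cannot be checked because the Kaplan-Meier curves are not shown. All of this concerns the primary endpoint; no event rate, effect size or power is stated for the key secondary.

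**3. Leverage of one event (hypothetical counts)**

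Inputs: n = 175 per arm, N = 350, a placebo events, b NTZ events, m = a + b. Unstratified Mantel-Haenszel statistic with continuity correction:

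χ² = (|a − m/2| − 0.5)² / V, with V = n²·m·(N − m) / [N²(N − 1)] = 0.25·m·(350 − m)/349.

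- 10 v 2: m = 12, V = 0.25 × 12 × 338/349 = 2.905; χ² = 3.5²/2.905 = 4.22; p = 0.040.
- 9 v 2: m = 11, V = 0.25 × 11 × 339/349 = 2.671; χ² = 3.0²/2.671 = 3.37; p = 0.066.

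Other starting points behave in the same way:

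| Counts (placebo v NTZ) | p | After losing one placebo event | p |
|---|---|---|---|
| 10 v 2 | 0.040 | 9 v 2 | 0.066 |
| 8 v 1 | 0.043 | 7 v 1 | 0.074 |
| 6 v 0 | 0.040 | 5 v 0 | 0.072 |

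The movement can go the other way: losing one NTZ event from 9 v 2 (p = 0.066) gives 9 v 1 (p = 0.025). Without the continuity correction, 10 v 2, 9 v 2 and 8 v 2 give 0.019, 0.032 and 0.055. Two lost placebo events are then needed to cross 0.05. The SAP specifies the correction, so the corrected values are the relevant ones.

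**4. Loss of power (assumed rates)**

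Let s be the fraction of true severe cases that are documented, equal in both arms. The observed risks are p₁ = s × placebo risk and p₂ = s × NTZ risk, and p̄ is their mean. Power, two-sided 0.05, no continuity correction:

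Φ{ [(p₁ − p₂) − 1.96·√(2p̄(1 − p̄)/175)] / √([p₁(1 − p₁) + p₂(1 − p₂)]/175) }.

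Example, placebo 6%, risk ratio 0.25, s = 1: (0.045 − 1.96 × 0.02031)/0.02017 = 0.26, so power is 0.60.

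| Assumed placebo risk, risk ratio | s = 1 | s = 0.8 | s = 0.5 |
|---|---|---|---|
| 2%, 0.5 | 0.12 | 0.10 | 0.08 |
| 4%, 0.25 | 0.44 | 0.36 | 0.24 |
| 6%, 0.25 | 0.60 | 0.51 | 0.34 |
| 10%, 0.25 | 0.83 | 0.73 | 0.52 |

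**The case against.** The plan does more to capture these events than the definition alone suggests. Amendment 1 added the room-air SpO2 route to what had been PaO2/FiO2 only, added retrieval of hospital values, and added follow-up of hospitalised subjects for the SAE narrative. Oxygen saturation is among the vital signs at the Day 4, 10, 22 and unscheduled visits, and resting breathlessness is asked about daily on Days 2-7. Deaths and COVID-19 admissions have their own CMH tests with odds ratios. All of this stands and limits the number of cases lost. It does not say how a death or an unrecorded value is classified in the key secondary.

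Four stronger readings are tempting, and the documents do not support them.

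- *Any subject put on oxygen is lost.* The definition has no timing restriction. A qualifying room-air value before oxygen, or a later PaO2/FiO2, counts.
- *The worst outcomes are scored as successes, and the treatment comparison is biased.* They would be non-events in one endpoint and are still reported in others. The trial is double-blind, and nothing in the plan suggests that record loss would differ by arm.
- *The primary and key secondary treat the same subject in opposite ways.* They measure different things: time to symptom response, and documented hypoxic severity. Hour 504 is also not clearly applied to every hospitalised subject. Protocol 9.4.1 applies it among subjects without a Sustained Response, and SAP 4.1.1 gives no precedence between its rows.
- *The entry criteria contradict the endpoint.* Exclusion criterion 1, "Persons with any clinical sign or symptoms suggestive of severe systemic illness with COVID-19, including the following" any one of four signs, is a screening rule for suggestive findings. It need not match an endpoint that confirms progression.

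Fragility to one event is also common to any rare-event test. That is fair, and it is a reason to classify the few events clearly.

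**Conclusion.** The gap is real and should be closed. Both documents require the two items together, neither has a death component, and no rule covers absent records. Applied as written, a COVID-19 death without both items on record, or a COVID-19 admission with no qualifying oxygenation value, does not meet the endpoint. That it would be counted as a non-event is the direct consequence of the wording and not a stated rule; leaving it to an unstated missing-data choice would be no better.

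The number of subjects affected cannot be judged from the documents. The expected effect is fewer events and less power, with chance imbalance second and systematic bias unlikely under blinding. The leverage figures rest on hypothetical counts, 175 per arm and an unstratified version of the planned test. The power figures rest on assumed event rates and equal documentation in both arms. Within those limits, one unrecorded placebo event can move the key secondary from p = 0.040 to p = 0.066.

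**What to change.** Before unblinding:

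1. In Protocol 9.3 and SAP 4.1.2, count death due to COVID-19 as progression to Severe COVID-19 Illness, whether or not breathlessness and oxygenation values are recorded. Use the same attribution as the exploratory mortality endpoint, and state how attribution is decided, since no rule is given now.
2. In SAP 4.2.2.1 and the table list in SAP 8.0, add a sensitivity analysis of the key secondary that also counts COVID-19 hospitalisations lacking a qualifying oxygenation record as progression.
3. Keep the current two-item definition as a supportive analysis.

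The cost is wording and two further tables from outcomes already collected. The downside is small: a few events without measured hypoxia are included. Oxygen-treated admission is better left out of the main definition, because the documents do not name oxygen use as a collected field and its use depends on local hospital practice.

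The same edit is an occasion to reconcile the analysis population. SAP 4.2.2 names ITT for this endpoint, while SAP 2.2.1 and Table 14.2.3 name ITI. The present point does not depend on that.
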